## V. STUDY PROCEDURES

Randomization and double-blind study treatment period to either placebo or LDM (1:1) of willing and eligible patients will occur at the end of the open label run-in phase per the parent CIRT protocol, and will be stratified by time since the qualifying event ( $< 6$  or  $\geq 6$  months from the date of MI or most recent angiogram), type of event (MI or multivessel CAD), presence of either type 2 DM or metabolic syndrome, and site, which will ensure balance in the proposed study. Patients willing to participate in CIRT will be asked to enroll into the sub-study and may sign the CIRT-CFR informed consent at any point between signing the parent CIRT informed consent and completing the parent CIRT randomization visit (Visit 4). After giving informed consent for the ancillary CIRT-CFR, patients will undergo the baseline PET scan along with echocardiography at any point between the parent CIRT post run-in visit (Visit 3) and up to 4 weeks after randomization (Visit 4). Per the parent CIRT protocol: i) blood will be collected and stored for biomarkers at baseline (Visit 3), ii) patients will complete quality of life (SF-36) questionnaires at enrollment (Visit 2) and 1-12 months (Visit 7) after randomization, and iii) patients will be called at 3, 6, and 10 months after randomization to assure compliance. Final PET scan and echocardiogram will occur at approximately 1-12 months after randomization or within 4 weeks ( $\pm 2$  weeks) of Visit 7. At that time, blood will be collected and stored for biomarkers (using the same protocol as in the parent CIRT) to coincide with follow-up imaging in CIRT-CFR. The data collection schedule for CIRT and CIRT-CFR is summarized in the Appendix. Trial schema is as follows:

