**Methods:** PET scans will be performed at the 3 imaging sites at randomization and at 1-12-month follow-up using a standardized study protocol. As described in section V, we have previously demonstrated feasibility of measuring myocardial blood flow with high reproducibility. In addition to CFR and coronary hemodynamics, we will also measure the total perfusion deficit (TPD) during stress and at rest, and calculate the difference TPD between stress and rest (reflecting total ischemic burden) using previously validated methods. The primary endpoint for the efficacy portion of *Aim 1* is the change in global CFR response to dipyridamole, reflecting primarily endothelium-independent coronary vasodilatation, over 1-12 months. A key secondary endpoint is the change in dipyridamole-stimulated TPDstress, reflecting the combined extent and severity of ischemia and scar, over 1-12 months. Tertiary endpoints include the change in hyperemic global and regional (i.e., non-infarcted myocardium)

myocardial blood flow (MBF), and the change in global and regional TPDstress-rest (reflecting the ischemia score) over 1-12 months.

**Statistical analyses:** For the analyses of both primary and secondary endpoints included in *Hypotheses 1 and 2*, we will use separate linear regression models with the respective change in global CFR (in response to dipyridamole) and TPDstress over 1-12 months as the outcome variables. Each of these regression models will control for baseline variables of stratum (DM or metabolic syndrome), time since index MI (< 6 months or ≥6 months), imaging site (BWH or OHI), the corresponding baseline global CFR score, as well as treatment assignment. Although we expect the distribution of change scores to be approximately normal, preliminary analyses will evaluate whether a transformation from the Box-Cox family will improve that assumption. From our experience in prior clinical trials using a similar design to CIRT-CFR, we expect a 10-15% attrition rate of patients due to death or loss to follow-up. Because it is not expected that site randomization assignment will influence these events, and because the available information is unlikely to allow for accurate imputation of missing values for CFR, subjects who do not have a repeat 1-12-month PET scan will not be included in the primary or secondary analyses.

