**Exploratory analyses:** The proposed ancillary study will not be powered to detect changes in clinical outcomes, patient symptoms, or changes in circulating biomarkers. However, we recognize the importance of exploring the correlations between the changes in CFR and LV function over the 1-12-month observation period and these meaningful outcomes. We propose the following exploratory tertiary objectives: (1) Explore an interaction between the change in CFR at 1-12 months with composite MACE that includes cardiac and all-cause mortality, recurrent MI, stroke, coronary revascularization, and hospitalization for unstable angina requiring unplanned revascularization or for congestive heart failure, occurring 3-4 years after randomization. We will use a proportional hazards model to explore relationships of CFR and its change with time until development of the first clinical event occurring through the end of randomization. We recognize that this exploratory analysis, in particular, will be limited because we expect only ~25 composite events in total in our study sample. (2) Correlate the change in CFR at 1-12 months with the corresponding change in QOL scores, as assessed by the standardized SF-36 Health Survey to be administered during enrollment, 12-month, and final study visits of the parent CIRT trial. Prior assessments with this tool have shown significant differences in baseline and 6-month follow-up scores in a modest-sized (n=120) patient population post-MI. (3) Correlate the change in CFR and LV function with the corresponding changes in circulating biomarkers of inflammation (hsCRP, IL-1) and myocardial strain (NTproBNP, hsTroponin), as assessed from stored biorepository samples at 8, 12 and 24 months after randomization. Analyses of changes in QOL scores and biomarkers will use linear regression models, after transforming changes to normality as necessary, and with control for baseline trial stratification variables, baseline QOL scores and biomarker levels, and treatment assignment. Main independent variables will be baseline and 1-12-month change in CFR. (4) Assess correlations among the baseline PET, echo, biomarker, and SF-36 data using linear regression models, as described above for continuous variables.

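### Type of qualifying event (MI or multivessel CAD) is a randomisation factor but is missing from the Hypothesis 1 to 3 models, which include the primary tests of both aims; adding it is a cheap gain in precision

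*Combined protocol and SAP*

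**What the plan says.** Section V (Study Procedures) says that 1:1 randomisation "will occur at the end of the open label run-in phase per the parent CIRT protocol". Allocation is "stratified by time since the qualifying event" and by three further factors: "type of event (MI or multivessel CAD), presence of either type 2 DM or metabolic syndrome, and site, which will ensure balance" in the sub-study. That makes four factors, with event type as one of them.

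Section VI, Aim 1, Statistical analyses, covers Hypothesis 1 (change in global CFR, the primary endpoint) and Hypothesis 2 (change in stress TPD, the key secondary endpoint). It says "Each of these regression models will control for baseline variables of stratum (DM or metabolic syndrome), time since index MI", split at 6 months, and then "imaging site (BWH or OHI), the corresponding baseline global CFR score, as well as treatment assignment". Section VI, Aim 2, Hypothesis 3 (change in GLS and in E', the two primary endpoints of that aim) opens its covariate list with the same words. It continues with imaging site, the baseline GLS or E' value and treatment. Neither list contains event type, and no reason is given.

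Two other sets of models are described more broadly. The Hypothesis 4 model, also under Aim 2, controls for the stratification variables without naming them. The quality-of-life and biomarker regressions under Exploratory analyses are fitted "with control for baseline trial stratification variables, baseline QOL scores and biomarker levels, and treatment assignment".

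**The concern.** When allocation is stratified on a factor that predicts the outcome, the treatment estimate varies less from trial to trial than a model without that factor assumes. The model's standard error is then larger than the true one, its intervals are wider than they need be, and the test rejects less often than its nominal level. Analysing by the factors used to randomise avoids this.

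The plan also looks uneven. On the ordinary reading of the text, the correlational and exploratory models carry the full set of stratification factors, while the models for the primary endpoints carry all but one.

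None of the listed covariates replaces event type. Section III admits patients on angiographic multivessel CAD with no MI, so time since index MI has no value for some patients and cannot separate the two event types.

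**Working it through.** **Inputs from the plan.** Section VI, Table 1 and its text: difference in change in CFR 0.24, SD 0.45, two-sided alpha 0.05, 130 evaluable patients (65 per arm at 1:1), 85% power. Section IV: 150 patients, 6 clinical sites.

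**Assumption.** R² is the share of the variance of the change score that event type explains. The documents give no value, so I use 0 to 0.10.

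**Step 1: the plan's own figure.** A two-sample t calculation with these inputs gives totals of 114, 130 and 150 for 80, 85 and 90% power, exactly as in Table 1. At 65 per arm:
- SE = 0.45 × √(2/65) = 0.0789
- 95% half-width = 1.96 × 0.0789 = 0.155
- power = Φ(0.24/0.0789 − 1.96) = 86.0% by the normal formula, and 85.5% by t

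This is an unadjusted comparison, so leaving out a covariate does not make it wrong.

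**Step 2: arms balanced on event type.** The true SE is 0.0789 × √(1 − R²), while a model without the factor still reports about 0.0789. Therefore:
- reported SE / true SE = 1/√(1 − R²)
- true size = 2 × [1 − Φ(1.96/√(1 − R²))]
- power without the term = Φ((0.24 − 0.155)/true SE)
- power with the term = Φ(0.24/true SE − 1.96)

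| R² | SE ratio | True size, term omitted | Half-width, omitted → adjusted | Power, omitted → adjusted |
|---|---|---|---|---|
| 0 | 1.000 | 5.0% | 0.155 → 0.155 | 86.0 → 86.0% |
| 0.02 | 1.010 | 4.8% | 0.155 → 0.153 | 86.2 → 86.7% |
| 0.05 | 1.026 | 4.4% | 0.155 → 0.151 | 86.6 → 87.7% |
| 0.10 | 1.054 | 3.9% | 0.155 → 0.147 | 87.3 → 89.3% |

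A simulation agrees (130 patients, an assumed 60% MI share, 20,000 runs for size and 10,000 for power). At R² = 0.10 the size is 3.6% without the term and 4.8% with it, and power is 87.3% against 89.7%.

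**Step 3: arms not balanced on event type.** In the same simulation with allocation that ignores event type:
- The model without the term keeps its size at 4.9 to 5.1% for R² from 0 to 0.10.
- Its SE is accurate: the mean reported and the empirical value are both 0.079.
- Power without and with the term is 84.9 and 84.7% at R² = 0, 84.7 and 86.4% at 0.05, and 85.5 and 88.7% at 0.10.

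**Step 4: which case applies.** Randomisation takes place in the parent trial. The factors give 2 × 2 × 2 × 6 = 48 cells, and 150/48 is about 3 patients per cell. Only patients who consent and are rescanned are analysed. Balance on event type in the analysed set may therefore be anywhere between the two cases.

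**The case against.** The best reply is that little is at stake. The documents offer no evidence that event type predicts change in CFR, stress TPD, GLS or E'. The planned models already adjust for a baseline value, which may absorb part of any such effect and which the calculations above leave out. If R² is near zero, nothing is lost. Any error in size is on the conservative side. A chance imbalance is also minor. With R² of 0.05 to 0.10 and an even split, the difference in mean change between event types is 0.45 × √(R²/0.25) = 0.20 to 0.28. A 10-point imbalance between arms would then move the CFR estimate by 0.02 to 0.03, against an SE of 0.079, and the unadjusted SE already allows for that. All of this stands as a limit on the consequence. None of it explains why one randomisation factor was left out.

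Four stronger readings are tempting, and the documents do not support them.
- **The factor is missing from every Aim 1 and Aim 2 model.** Hypothesis 4 belongs to Aim 2 and refers to the stratification variables. The plan presents that model as an extension of a primary model, so the phrase could be shorthand for the shorter list. The text does not settle this, but it does not show an omission there.
- **The intervals are too wide.** That needs both a predictive factor and balanced arms in the analysed set. The sparse-cell argument, which casts doubt on balance, works against it.
- **Stress TPD must suffer most because MI means scar.** Section III allows a qualifying MI to be documented from hospital records or Q waves, without imaging of scar. The endpoint is also a change, so stable scar present at both scans would largely cancel.
- **The primary tests are invalid, or 130 patients are too few.** Steps 1 to 3 show neither.

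**Conclusion.** The omission is certain from the text for Hypotheses 1, 2 and 3. Its effect is conditional and small. With R² assumed between 0 and 0.10, the reported CFR standard error is 0 to 5% too large and the true size is 5.0 to 3.9% if the analysed arms are balanced on event type; if they are not, standard error and size are right. In both cases adjustment gains about 0 to 3 points of power. False positives are not inflated. The figures were worked for CFR; for the other endpoints the SE ratio and true size depend on R² in the same way, with R² equally unknown. This is a free improvement rather than the repair of an invalid analysis.

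**What to change.** In section VI, add type of qualifying event (MI or multivessel CAD), with the value recorded at the parent trial's randomisation, to the covariates of the Hypothesis 1 and 2 models under Aim 1 and the Hypothesis 3 models under Aim 2. Make the change before unblinding, so that it cannot be read as choosing a model after seeing results. The cost is one degree of freedom out of about 130 and one line of text; the data are already held. Softening the claim in section V that stratification guarantees balance would be an editorial change and is not needed for this fix.

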#### **Inclusion criteria:**

- a. Age  $\geq 18$  years at screening;
- b. Documented past history of MI OR past evidence of multivessel CAD by angiography, completed any planned coronary revascularization associated with a qualifying event at least 60 days prior to enrollment, and clinically stable for  $\geq 60$  days prior to enrollment; qualifying prior MI must be documented either by hospital records, evidence on current ECG of Q waves in 2 contiguous leads, and/or an imaging test demonstrating wall motion abnormality or scar; qualifying evidence of multivessel CAD by angiography must be documented by CAD in at least two major epicardial vessels defined either as the presence of a stent, a coronary artery bypass graft, or an angiographic lesion of 60% or greater (left main CAD that has been revascularized with a stent or bypass graft will qualify as multivessel disease, as will the presence of a 50% or greater isolated left main stenosis);
- c. History of type 2 DM or metabolic syndrome (meeting 2004 AHA/NHLBI definition\*) at time of study enrollment; \*includes any 3 of the following 5 diagnostic criteria: waist circumference  $\geq 102$  cm in men or 88 cm in women; triglycerides  $\geq 150$  mg/dl or on drug treatment for elevated triglycerides; high-density lipoprotein cholesterol (HDL-C)  $< 40$  mg/dL in men or  $< 50$  mg/dL in women or on drug treatment for reduced HDL-C; systolic blood pressure  $\geq 130$  mm Hg or diastolic blood pressure  $\geq 85$  mm Hg or on drug treatment for hypertension; and elevated fasting glucose  $\geq 100$  mg/dL or on drug treatment for elevated glucose.
- d. Willingness to participate as evidenced by signing the CIRT and CIRT-CFR informed consent.

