**IV. SUBJECT ENROLLMENT**

We propose to recruit 150 patients for CIRT-CFR. This will be a collaborative effort between 6 clinical sites, with 4 sites in the Boston area: (1) *Brigham and Women's Hospital, BWH* (PI: [name]), (2) *Joslin Diabetes Center* (PI: [name]), (3) *Massachusetts General Hospital* (PIs: [name], and [name]), (4) *North Shore Medical Center* (PI: [name]), and two additional sites in the Ottawa area: (5) *Ottawa Heart Institute, OHI* (PI: [name]), and in Birmingham, Alabama: (6) *University of Alabama, UAB* (PI: [name]). We will have 3 imaging sites (BWH, PI: [name] [name]; OHI, PI: [name]; and UAB, PI: [name]), with **BWH serving as the Core Imaging Lab**, and all 4 Boston area sites referring patients for imaging to BWH. The subjects of the trial will be patients with CAD and type 2 DM or metabolic syndrome enrolled in the parent study (CIRT) and recruited from participating

CIRT sites local to BWH, OHI, and UAB. All patients identified at the 6 participating clinical sites as being potentially eligible for CIRT are automatically eligible for participation in this ancillary study.

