## VI. BIOSTATISTICAL ANALYSIS

CIRT-CFR sites participating in the proposed ancillary study. Based on our power analysis and sample size calculations, we estimate that each of the 6 clinical sites will be required to enroll approximately 25 patients over approximately 3 years. This is equivalent to 1 patient every 6 weeks per site, which we believe is reasonable and attainable. All sites have received IRB approval for the parent study and are actively enrolling patients in the parent CIRT trial. The proposed imaging studies (PET scans and echos) are routinely performed at the 3 imaging sites (BWH, OHI, and UAB). Drs. [name] (PI) and [name] (both at BWH), [name] (OHI), and [name] (UAB) are recognized experts in quantitative PET imaging and echocardiography, have published widely on these topics, and have extensive experience in conducting clinical trials using imaging endpoints.

***Aim 1. To test the hypothesis that systemic inflammation is a critical determinant of coronary flow reserve (CFR) and myocardial tissue perfusion, as assessed by quantitative PET imaging, in stable CAD patients with type 2 DM or metabolic syndrome.*** Specifically, we propose that treatment with LDM at a target dose of 15 to 20 mg orally weekly for 1-12 months will, compared to placebo, result in:

***Hypothesis #1:*** Improved global CFR in response to dipyridamole, reflecting primarily endothelium-independent vasodilation.

***Hypothesis #2:*** Reduced total stress perfusion deficit, a semi-quantitative score combining scar and ischemia.

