**Methods:** 2-D echocardiograms will be performed at the 3 enrolling imaging sites at baseline and 12 months after randomization in accordance with standard clinical practice and utilizing a standardized study protocol as outlined in section V. As described in section V, we have previously demonstrated feasibility of measuring cardiac mechanics with high reproducibility. The primary efficacy endpoints for *Aim 2* are the change in LV peak global longitudinal strain (GLS) (systolic function) and in tissue Doppler mitral annular early diastolic relaxation velocity (E') (diastolic function). Key secondary endpoints are change in other LV systolic function measures (LVEF and tissue Doppler peak systolic mitral annular velocity (S')), as well as change in other LV diastolic function measures (LV early diastolic strain rate by speckle-tracking, and mitral inflow Doppler E velocity to E' ratio (E/E')). Tertiary endpoints include changes in more conventional measures of LV structure (e.g. volumes, wall thickness, mass) over 1-12 months.

**Statistical analyses. Hypothesis 3:** We will use separate linear regression models with the respective change in LV peak GLS and E' over 1-12 months as the outcome variables. Each of these regression models will control for baseline variables of stratum (DM or metabolic syndrome), time since index MI (< 6 months or ≥ 6 months), imaging site (BWH, OHI, or UAB), the corresponding baseline LV peak GLS and E' scores, as well as treatment assignment.

**Hypothesis 4:** Although temporality cannot be established in correlational analysis of concurrent changes, we will also use regression models to clarify the association of changes in CFR and LV function. Controlling for treatment assignment, baseline stratification variables, baseline CFR and LV function, as well as change in LV function, our outcome will be change in CFR. By adding the baseline and change in LV function to our primary model for *Aim 2*, we will explore whether changes in CFR are associated with changes in LV function, or whether independent treatment effects remain.

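### The Aim 1 regression covariates do not fit the design: UAB is missing from imaging site, time since MI is undefined for patients without an MI, and baseline TPDstress is not named

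*Combined protocol and SAP*

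**What the plan says.** Section VI, Aim 1, Statistical analyses, specifies separate linear regressions for change in global CFR (primary) and change in TPDstress (key secondary). A single covariate list applies to both: diabetes or metabolic syndrome stratum, treatment assignment, and "time since index MI (< 6 months or ≥6 months), imaging site (BWH or OHI), the corresponding baseline global CFR score".

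Other parts of the plan bear on each item:

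- **Imaging site.** Aim 1, Methods: "PET scans will be performed at the 3 imaging sites at randomization and at 1-12-month follow-up". The opening of Section VI says the scans "are routinely performed at the 3 imaging sites (BWH, OHI, and UAB"). The Aim 2 model (Hypothesis 3) lists "imaging site (BWH, OHI, or UAB), the corresponding baseline LV peak GLS". Section IV has "all 4 Boston area sites referring patients for imaging to BWH", so six clinical sites feed three imaging sites.
- **Time term.** Section III admits patients with "Documented past history of MI OR past evidence of multivessel CAD by angiography". Section V stratifies randomization by time since the qualifying event, dichotomized at six "months from the date of MI or most recent angiogram), type of event (MI or multivessel CAD"), and also by diabetes/metabolic syndrome and site. The Aim 2 model repeats the time-since-MI wording.
- **Baseline value.** The Aim 2 model names the baselines of both its outcomes, GLS and E'. The Aim 1 sentence names only global CFR.
- **Event type.** It is a randomization stratum, but it is in neither the Aim 1 list nor the Aim 2 Hypothesis 3 list. The exploratory models are to be fitted "with control for baseline trial stratification variables, baseline QOL scores and biomarker levels, and treatment assignment", and the Hypothesis 4 model also controls for the stratification variables.

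**The concern.** The stated covariates cannot be applied literally to every randomized patient. A UAB patient has no level of the site factor, and a patient who never had an MI has no value for the time factor. The analyst would have to choose a coding, and more than one is possible. UAB could be a third level or pooled with another site. Patients without an MI could be coded from the angiogram date, placed in the later category, given a category of their own, or dropped by default software handling of missing values.

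These choices sit in the primary-endpoint model and can move its estimate, so they should be fixed before anyone sees unblinded data. Imaging site is a substantive covariate for a PET endpoint: Section V allows two flow tracers, and Section VII speaks of sites that use rubidium.

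For TPDstress the issue is precision. Read literally, the model adjusts for a different variable and leaves out the outcome's own baseline.

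**Working it through.** **1. The plan's own figures (Table 1).** Inputs: CFR difference 0.24, SD 0.45; TPDstress difference 2.5, SD 4.9; two-sided alpha 0.05 (Section VI, Power calculations); 1:1 allocation (Section V). Method: two-sample t-test with noncentrality δ/(SD·√(4/N)) and N − 2 degrees of freedom.

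| Outcome | N | Power |
|---|---|---|
| ΔCFR | 130 | 85.5% |
| ΔTPDstress | 124 / 140 / 164 | 80.5% / 85.0% / 90.1% |
| ΔTPDstress | 130 | 82.3% |

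Table 1 reproduces. It is an unadjusted calculation, so no correction to the covariate list changes it.

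**2. Patients with no site level.** UAB is one of six clinical sites at about 25 patients each (Section VI): 25 of 150 randomized, or 130/6 ≈ 22 of 130 evaluable.

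**3. Patients with no value on the time term.** The plan does not give the share of patients without an MI, so no count can be stated. Section III makes it possible for the share to be above zero.

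**4. TPDstress power under the two readings, N = 130.** The plan gives no correlations, so the following are assumptions. Let ρ be the correlation between baseline and follow-up TPDstress, with equal variances at the two times.

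- *Own baseline:* residual SD = 4.9·√((1+ρ)/2).
- *Baseline CFR only, as written:* let r be the size of the correlation between baseline CFR and baseline TPDstress, and assume baseline CFR acts only through baseline TPDstress. The squared correlation of baseline TPDstress with its change is (1−ρ)/2, so R² = r²(1−ρ)/2 and residual SD = 4.9·√(1−R²).

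| | ρ = 0.5 | ρ = 0.8 |
|---|---|---|
| Own baseline | SD 4.24, 91.5% | SD 4.65, 86.1% |
| Baseline CFR only, r = 0 | SD 4.90, 82.3% | SD 4.90, 82.3% |
| Baseline CFR only, r = 0.5 | SD 4.74, 84.6% | SD 4.84, 83.2% |

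Matched on ρ, own-baseline adjustment gains about 7 to 9 percentage points at ρ = 0.5 and about 3 to 4 at ρ = 0.8.

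**5. Adding event type.** If it explained 5% of the variance in ΔCFR (assumed), the SD becomes 0.45·√0.95 = 0.439 and power at 130 goes from 85.5% to 87.2%. If it explained none, power stays at 85.5%. Leaving it out does not inflate type I error.

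**6. Degrees of freedom.** The Aim 1 model as written has six parameters (intercept, treatment, stratum, time, one site contrast, baseline), so 130 − 6 = 124 error degrees of freedom. A third site level and event type leave 122. With CFR adjusted for baseline at ρ = 0.8 (SD 0.45·√0.9 = 0.427), power is 88.88% against 88.87%.

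**The case against.** The strongest reply is that these are drafting slips any competent analyst would repair. The site list looks like leftover two-site wording; it states no exclusion, and the Methods paragraph just above it says three sites. The time term uses the same six-month cut as the randomization stratum, which was recorded for everyone randomized, so it is probably shorthand for that stratum. The word corresponding, and the parallel Aim 2 sentence, suggest that each outcome's own baseline was intended. Event type is optional. No stated sample size or power changes, and no rule drops anyone.

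Much of this stands. The probable intent is clear, and power losses computed by deleting UAB patients or patients without an MI would rest on an exclusion the plan never states; they are not used here. Event type is a recommendation and not an error.

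The reply does not remove the point. The current text of the primary model contradicts the Methods paragraph above it and the Aim 2 model. Nowhere does the plan say that time since MI means time since the qualifying event. A fix that everyone would agree on is still not written down. The Hypothesis 4 and exploratory wording on stratification variables supports adding event type, since those models already call for it.

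**Conclusion.** The concern holds. The Aim 1 list conflicts with the design on imaging site and on the time term, and it does not name the baseline of the key secondary outcome. About 25 of 150 randomized patients (about 22 of 130 evaluable) have no site level, and an unknown number of patients without an MI have no value on the time term. The time-term fault is also in the Aim 2 model.

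The sample size and Table 1 stand. The only calculated cost is precision for TPDstress: about 3 to 9 points of power at 130 evaluable, under assumed values of ρ from 0.5 to 0.8 and r from 0 to 0.5. The larger reason to act is that the coding of the primary model should not be left to choice after unblinding. This should be fixed, but it does not threaten the design.

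**What to change.** In Section VI, Aim 1, Statistical analyses, replace the covariate sentence with wording such as:

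> Covariates in each model are treatment assignment; diabetes or metabolic syndrome stratum; time since qualifying event (MI or most recent angiogram; under 6 months, or 6 months and over); type of qualifying event (MI or multivessel CAD); imaging site (BWH, OHI, UAB); and the baseline value of that model's outcome (global CFR for change in CFR, TPDstress for change in TPDstress).

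In the Aim 2 Hypothesis 3 model, change the time term in the same way and add type of qualifying event. Event type is the recommended addition; the other changes are corrections. State also that imaging site represents the randomization factor site, because the four Boston clinical sites all image at BWH. This is a modelling choice the plan does not currently make, and the sponsor should confirm it. Date the change before unblinding.

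The cost is wording only, since every variable is already recorded at randomization or at the baseline scan. Aim 1 uses two more degrees of freedom and Aim 2 one; at 130 evaluable patients this changes power by less than 0.1 percentage point.
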